ID: H-22063621

Protocol GA-18

Title: The role of endogenous GIP in glucose metabolism during fasting

ID: H-22063621

Date: 10/04/2024

Introduction

The incretin hormone, glucose-dependent insulinotropic polypeptide (GIP), is secreted from enteroendocrine K cells in the small intestine following food. GIP have a powerful effect on glucose-induced insulin secretion from pancreatic beta cells, the incretin effect. GIP accounts for about 45 % of insulin secretion after food intake. Exogenous GIP during fasting stimulates glucagon secretion in low blood glucose and has an anabolic effect in/on fat and bone metabolism in healthy individuals. However, we do not fully understand the physiological role of GIP and with this study, we will investigate how endogenous GIP affects the body during fasting.

Purpose

The purpose of this project is to investigate the effects of endogenous GIP in healthy, obese individuals. With the infusion of the GIP receptor antagonist (GIP(3-30)NH₂) is it possible to describe the effects of endogenous GIP, by comparing with what happens during a saline infusion (placebo)

Hypothesis

We hypothesize that endogenous GIP has physiological effects in fasting and that we will see a decrease in glucagon levels during GIP(3-30)NH₂ infusion compared to placebo.

Study design

In a randomized, placebo-controlled, double-blind, crossover design comprising two experimental days, 12 participants will receive 180-minute infusions of GIP(3-30)NH₂ (800 pmol/kg/min) and placebo (saline) in a randomized order respectively, after observed 10 hours fast. An *ad libitum* meal be served at time 180 min, during continuous infusion. To keep the infusate content hidden for the investigator and the participants, the preparation of the infusate during the experimental days will be handled by an employee otherwise not involved in the study. During the trial, the participant assesses and records current appetite and thirst on standardized VAS forms. Blood pressure and heart rate are measured at time: -30 min, 0 min, 30 min, 60 min, 90 min, 120 min, 150 min and 180 min. Blood samples (0,2 ml) are taken at time: -30 min, -20 min, 0 min, 15 min, 30 min, 60 min, 90 min, 120 min, 150 min and 180 min. Brown adipose tissue activity is measured with thermal camera, and resting metabolic rate is determined with indirect calorimetry.

Calculations and statistics

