Data will be processed and presented using standard descriptive statistics. Baseline-substracted and absolute values for AUC will be calculated using numerical integration. The GIP(3-30)NH₂ effect is calculated for a given endpoint as a percentage of the placebo infusion: Effect = 100 – (GIP(3-30)NH₂ / placebo)

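### The percent-of-placebo effect is not restricted to absolute AUC; on baseline-subtracted fasting AUC the placebo denominator can be near zero or negative, so the percentage can be unstable or reverse sign

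*Combined protocol and SAP*

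**What the plan says.** In Calculations and statistics, one sentence plans two kinds of AUC: "Baseline-substracted and absolute values for AUC will be calculated using numerical integration". The next sentence defines the effect: "The GIP(3-30)NH₂ effect is calculated for a given endpoint as a percentage of the placebo infusion". The formula is printed as "Effect = 100 – (GIP(3-30)NH₂ / placebo" followed by a closing bracket. This is the only treatment contrast in the section. Nothing limits it to one kind of AUC, and no rule covers a placebo value that is zero, near zero or negative. The section does not define baseline. It also does not say whether percentages are formed per participant and then averaged, or formed once from group means.

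Study design sets the conditions. The antagonist or saline is infused "after observed 10 hours fast", with the "meal be served at time 180 min, during continuous infusion". Sampling is described as "Blood samples (0,2 ml) are taken at time: -30 min, -20 min, 0 min", then at 15, 30, 60, 90, 120, 150 and 180 min. The Hypothesis section is directional: "we will see a decrease in glucagon levels during GIP(3-30)NH₂ infusion compared to placebo".

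**The concern.** A percentage of placebo is meaningful only when the placebo value is positive and well away from zero. Absolute AUC of a hormone or metabolite meets that condition. Baseline-subtracted (net) AUC over a fasting saline infusion does not: no meal or other stimulus is planned in the sampled window to move the placebo curve clearly off its baseline. The denominator is then whatever the curve drifts over three hours, plus measurement noise, and it can take either sign.

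At stake is the reported direction and size of the effect. The hypothesis predicts a fall in glucagon. Applied to net AUC, the percentage could show a rise when glucagon fell, or a fall of several hundred percent.

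**Working it through.** The documents give no placebo values, standard deviations, expected effect or sample size calculation, so there is no planned figure to reproduce. The check has an algebraic part, which needs no assumed data, and a simulation part, which does.

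**Inputs from the documents.** Sampling times, saline comparator, fasting window ending at the 180-min meal, 12 participants in a two-period crossover, both AUC types, and the effect formula.

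**Reading of the formula.** As printed, an antagonist/placebo ratio of 0.90 gives 100 − 0.90 = 99.1, not 10%. The evident intention is 100 − 100 × A/P, which is used below.

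**Algebra.** 100 − 100 × A/P = −100 × (A − P)/P. For a fixed difference A − P = −200:
- P = +100: −100 × (−200)/100 = +200%
- P = +10: −100 × (−200)/10 = +2000%
- P = −100: −100 × (−200)/(−100) = −200%

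A positive value is meant to denote a decrease, so the last line reports an increase although the antagonist value is lower by the same amount.

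**Both AUC types side by side.** Set baseline to 100 and let the antagonist lie 10 units below placebo on average over 180 min. In the first row below, net P = 180 × 10 = 1800 and net A = 0, giving 100%. Absolute P = 180 × 110 = 19,800 and absolute A = 180 × 100 = 18,000, giving 100 − 100 × 18,000/19,800 = 9.1%.

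| Mean placebo change | Effect on net AUC | Effect on absolute AUC |
|---|---|---|
| +10 | +100% | 9.1% |
| +1 | +1000% | 9.9% |
| +0.1 | +10,000% | 10.0% |
| −1 | −1000% | 10.1% |
| −5 | −200% | 10.5% |
| −10 | −100% | 11.1% |

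The paired difference in net AUC is −10 × 180 = −1800 unit·min in every row.

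**Simulation of single participants.** Assumptions: baseline is the mean of the −30, −20 and 0 min samples; independent sample noise has CV 5–15%; placebo drifts linearly; the antagonist lowers the value by a further 20% of baseline at 180 min, about 10% on average. With a flat placebo the net denominator is negative in 50% of participants. The central 95% range of the effect on net AUC is −4538% to +4941% at CV 5% and −1756% to +1941% at CV 15%. On absolute AUC the ranges are 4.9 to 14.9% and −6.2 to 24.0%.

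**Simulation of whole trials.** 20,000 trials of 12 per scenario. Assumptions: true 20% decrease reached linearly over 30 min, between-person CV 30%, day CV 10%, sample CV 5–15%. The share of trials in which the effect on net AUC has the wrong sign is:

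| Placebo drift by 180 min | Mean of individual percentages | Ratio of group means | Median of group ratio |
|---|---|---|---|
| 10% fall | 50–82% | 95–100% | −321% to −348% |
| Flat | 36–45% | 50% | not meaningful |
| 10% rise | 13–24% | 0–5% | 362–386% |
| 20% rise | 1–15% | about 0% | about 203% |

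The medians agree with a noise-free check. A 20% decrease with a 30-min ramp averages 20 × 165/180 = 18.3% over the window. A 10% linear drift averages 5%. Then 100 × 18.3/5 is about 367%, with the sign set by the drift.

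Over drifts of 0 and ±10%, the geometric mean ratio of absolute AUC gave about 18% (5–95% range 12–24%), which matches that 18.3%. The mean paired difference in net AUC had the wrong sign in 0.0% of trials. With true decreases of 10% or 30%, the group-ratio wrong-sign rates were similar: flat 48–51%, 10% fall 93–100%, 10% rise 0–5%.

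**The case against.** The strongest reply is that the section never says the percentage will be computed on net AUC. The hypothesis concerns glucagon levels, which absolute AUC answers directly and safely. This is fair: the gap is a missing restriction, not a stated misuse. But the unrestricted sentence directly follows the one naming both AUC types, so a reader following the plan would apply it to both.

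Second, the analysis is descriptive, no test or decision rule depends on the percentage, and an absurd value would be noticed beside the AUCs themselves. This stands, and it limits the consequence to reporting. It does not help with a plausible-looking value of the wrong sign.

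Third, sign reversal depends on restoring the missing factor of 100. This is correct. Under the printed formula the result moves to either side of 100 instead: in the side-by-side example it is 109, 199 and 89 for placebo changes of +1, +0.1 and −1. The instability remains.

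Fourth, the simulated sizes rest on assumed effect, noise and drift, and depend heavily on drift, whose direction is unknown. This also stands; the figures are illustrative, and the algebra carries the point.

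Finally, the paired difference is not immune to noise. With a 10% true effect and 15% sample CV it has the wrong sign in about 1–2% of trials. That is small next to the rates for the percentage with a flat or falling placebo.

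**Conclusion.** The concern holds. As written, the rule covers an endpoint for which it is not a valid measure, in a design that gives the placebo denominator no reason to be away from zero. Instability near zero follows from the formula alone; sign reversal follows once the factor of 100 is restored. How often it would occur cannot be known from the documents. Under the stated assumptions, the wrong-sign rate for the ratio of group means runs from about 0% (20% placebo rise) through 50% (flat) to 95–100% (10% fall), and even where the sign is right the size is greatly inflated. Absolute AUC is unaffected. This is a correctable reporting problem that should be fixed before the results are summarised; it does not undermine the design.

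**What to change.** Add one or two sentences to Calculations and statistics:
- Restrict the percent-of-placebo effect to absolute AUC and other strictly positive ratio-scale endpoints. One suitable form is 100 × (1 − geometric mean of the within-participant antagonist/placebo ratios); other ratio summaries of absolute AUC would also serve if specified.
- For baseline-subtracted AUC, and any endpoint that can be zero or negative, report the within-participant difference (antagonist minus placebo) in native units with a 95% CI.

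The same edit can define baseline and restore the factor of 100.

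No new data are needed, because the crossover already supplies the pairs. There are two small costs: endpoints will no longer all share one percentage scale, and a percentage on absolute AUC is not adjusted for day-to-day differences in baseline.

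### The plan does not say how the active/placebo ratio is aggregated over participants; if individual ratios of a positive endpoint are averaged, a fall in glucagon is understated

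*Combined protocol and SAP*

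**What the plan says.** The statistical plan is the short section Calculations and statistics.

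- **Summary method:** "Data will be processed and presented using standard descriptive statistics". The section names no model, test, significance level or interval.
- **Endpoint scale:** AUC is planned in two forms, baseline-subtracted and absolute; these "values for AUC will be calculated using numerical integration".
- **Effect measure:** the antagonist's effect is expressed "for a given endpoint as a percentage of the placebo infusion", with the formula "Effect = 100 – (GIP(3-30)NH₂ / placebo" (closing bracket omitted here). As printed, the ratio is not multiplied by 100.

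The Study design section describes a "randomized, placebo-controlled, double-blind, crossover design comprising two experimental days", in which "12 participants will receive 180-minute infusions" of each treatment. Each participant therefore contributes one active and one placebo value per endpoint. The Hypothesis section gives a direction: "we will see a decrease in glucagon levels" on the antagonist compared with placebo. It gives no size for the fall. No variability figure appears anywhere in the documents.

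**The concern.** A ratio can be carried from 12 pairs of values to one result in several ways: the mean of individual ratios, their median, the ratio of arm means, or the geometric mean ratio. These estimate different things, and the plan does not choose among them.

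In a crossover with a percentage effect and descriptive statistics, one natural reading is a ratio per participant, then an arithmetic mean. For a positive endpoint that choice has a known bias. Noise in the denominator pushes the mean ratio up, so a fall is understated, and with no true effect the expected result is a small rise. This runs against the direction that the trial hypothesises. The measure is also asymmetric: exchanging the two treatments does not give the reciprocal result.

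Baseline-subtracted AUC has a different problem. Its values can be near zero or negative, so dividing by the placebo value may give no usable number.

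**Working it through.** **Inputs from the documents:** two-period crossover, n = 12, effect defined as active over placebo, hypothesised direction a fall. The plan states no figure that could be reproduced.

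**Assumed inputs (not in the documents):** within-person CV *c* of 10%, 20% or 30%; true fall of 15% (θ = 0.85); lognormal errors, independent between the two days unless stated; between-person CV of 40%, which cancels from individual ratios.

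**Step 1. Expected individual ratio.** Write active = b·θ·e₁ and placebo = b·e₂, where b is the person's own level and e₁, e₂ are day errors with log-variance s² = ln(1 + c²). Then ln(active/placebo) has mean ln θ and variance 2s², so

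E(active/placebo) = θ·exp(s²) = θ·(1 + c²).

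**Step 2. Numbers, with the effect read as 100 − 100 × ratio.**

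| CV | Mean ratio, no effect | Mean ratio, true 15% fall | Fall as reported |
|---|---|---|---|
| 10% | 1 + 0.01 = 1.01 | 0.85 × 1.01 = 0.8585 | about 14.1% |
| 20% | 1 + 0.04 = 1.04 | 0.85 × 1.04 = 0.884 | 11.6% |
| 30% | 1 + 0.09 = 1.09 | 0.85 × 1.09 = 0.9265 | about 7.4% |

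Simulation of 12-participant trials agrees. With no effect, the standard error of the mean ratio is about 4.1, 8.5 and 13.6 percentage points, so shifts of 1, 4 and 9 points are about 0.2, 0.5 and 0.7 standard errors. The mean ratio exceeds 1 in about 59%, 67% and 74% of such trials, where 50% would be expected without bias.

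**Step 3. Correlated day errors.** With correlation ρ between the two days' log errors, the factor becomes exp{s²(1 − ρ)}. At CV 20% it is 1.040 for ρ = 0, 1.020 for ρ = 0.5 and 1.000 for ρ = 1. For non-negative correlation, 1 + CV² is therefore an upper value.

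**Step 4. Other ways of aggregating, no effect.** The ratio of arm means is off by about 0.1, 0.4 and 0.9 points at CV 10%, 20% and 30%. The geometric mean ratio is off by about 0.1, 0.3 and 0.75 points. At CV 20% the median of individual ratios averages about 1.005.

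**Step 5. Power, for an assumed test.** The plan names no test. For a two-sided 5% one-sample t-test with n = 12 and a true 15% fall:

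| CV | Raw ratios against 1 | Log ratios against 0 |
|---|---|---|
| 10% | 93% | 95% |
| 20% | 36% | 45% |
| 30% | 16% | about 24% |

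At CV 20% a paired t-test on untransformed differences has about 40%. With no effect and CV 30%, the raw-ratio test declares an increase in about 4.2% of trials and a decrease in about 1.4%, where each should be 2.5%.

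**Step 6. Baseline-subtracted AUC.** This was simulated as normal values with the same mean on both days and no effect. With mean/SD = 0, the mean of 12 ratios has 5th to 95th percentiles of about −6.3 to 6.3 and lies below 1 in 75% of trials. With mean/SD = 1, the range is about −4.9 to 6.3, and 60% lie below 1. With mean/SD = 3, only about 24% lie below 1. The direction depends on where the values sit relative to zero.

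**Step 7. The formula as printed.** With no effect it gives 100 − 1 = 99; with a 20% fall it gives 100 − 0.8 = 99.2. The figures above therefore assume that a factor of 100 on the ratio was intended, as the accompanying wording about a percentage implies.

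**The case against.** A reader might infer that the planned measure is biased as it stands. The documents do not support that. They do not say that ratios are formed per participant or averaged arithmetically. A ratio of arm means or a median fits the text too, and on those readings the bias nearly disappears (Step 4). What the text establishes is silence on aggregation; the bias follows under one reading. This objection stands, and the point is made conditionally for that reason.

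A reader might also infer that a ratio of arm means would throw away the pairing. That does not follow. An interval computed by participant (Fieller, delta method or bootstrap over participants) keeps it, and the plan specifies no interval.

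Three further limits stand:

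- The power and error-rate figures belong to a test that the plan does not contain. They illustrate the choice and do not describe planned operating characteristics.
- The size rests on CVs that the documents do not give. At CV 10% or less the shift is about 1 point or less, and at every CV shown it is smaller than one standard error.
- The upward direction cannot be extended to baseline-subtracted AUC. Nor can the printed formula show a rise for any realistic ratio, because it lacks the factor of 100. That omission is a separate and more certain error.

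The objection does not remove the case for a change. The plan leaves a choice open, one natural way of making it works against the trial's own hypothesis, and a better-behaved measure is available from the same data.

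**Conclusion.** The point holds in conditional form. The plan defines a ratio without saying how it is aggregated over 12 participants. If individual ratios of a positive endpoint are averaged arithmetically, the result is too high by a factor of up to about 1 + CV². The consequence is negligible at a CV of 10% (a 15% fall reads as about 14.1%) and material at 20% to 30% (11.6% and about 7.4%). For an assumed t-test at CV 20%, power is 36% on raw ratios against 45% on log ratios.

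These sizes rest on assumed CVs, an assumed 15% fall, lognormal errors and independence between days; positive correlation between the days' errors makes the bias smaller. For baseline-subtracted AUC the defect is instability of the ratio, with no fixed direction of bias. The change is worth making before analysis, because it settles an undefined estimate at almost no cost.

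**What to change.** In Calculations and statistics, replace the effect formula with a defined summary for each scale:

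- **Positive endpoints (for glucagon, absolute AUC over 0 to 180 minutes):** take the within-participant difference in log values, active minus placebo. Average it, back-transform to a geometric mean ratio with a 95% CI, and report the effect as 100 × (1 − geometric mean ratio) percent. This also supplies the missing factor of 100.
- **Baseline-subtracted AUC:** report the within-participant difference, active minus placebo, with a 95% CI, and no ratio.

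The cost is a sentence or two and no extra data. Results for positive endpoints will be geometric rather than arithmetic means, which the report should state. The log method applies only to positive values, which is why baseline-subtracted AUC needs its own rule.

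### The plan's only effect formula lacks the factor of 100 its wording calls for, so no effect reads as 99 instead of 0

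*Combined protocol and SAP*

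**What the plan says.** The Calculations and statistics section plans descriptive statistics and two kinds of AUC: "Baseline-substracted and absolute values for AUC will be calculated using numerical integration". The next sentence defines the effect: "The GIP(3-30)NH₂ effect is calculated for a given endpoint as a percentage of the placebo infusion". The formula that follows is "Effect = 100 – (GIP(3-30)NH₂ / placebo", and the bracket closes straight after the word placebo. No multiplication by 100 and no percent sign appears.

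The documents contain no other effect formula, no worked example and no expected value that would show which scale was meant. The Hypothesis section gives only the expected direction for glucagon: "we will see a decrease in glucagon levels during GIP(3-30)NH₂ infusion compared to placebo".

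**The concern.** The sentence and the formula use different scales. The sentence promises a percentage. The formula takes 100, which is on the percent scale, and subtracts a ratio, which is on the unit scale. Applied as printed to an absolute AUC, every plausible result lands just below 100, and an increase under the antagonist still reads as a large positive effect. The predicted fall in glucagon would be almost indistinguishable from no effect or from a rise.

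A second difficulty comes from the scope of the formula. It covers any endpoint, and nothing excludes the baseline-subtracted AUCs planned in the sentence before it. Participants fast until the meal at 180 min, so a baseline-subtracted AUC under saline can plausibly be close to zero or below it. Such a value is a poor denominator, with or without the factor of 100.

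What is at stake is a wrong or ambiguous reported summary. The values under each infusion remain available, so the hypothesis can still be tested and the percentage recalculated.

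**Working it through.** **Inputs.** The printed formula, the stated percentage scale and the two kinds of AUC all come from Calculations and statistics. The plan gives no numerical effect, so there is no figure of its own to reproduce. Write r = value under GIP(3-30)NH₂ / value under placebo.

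- Printed formula: 100 − r
- Percentage reduction that the wording points to: 100 × (1 − r) = 100 − 100r

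**Absolute values (placebo positive).** At r = 1 the printed formula gives 100 − 1 = 99, and the percentage form gives 100 × (1 − 1) = 0. For other ratios:

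| r | Printed: 100 − r | Percentage: 100 × (1 − r) |
|---|---|---|
| 0 | 100 | 100 |
| 0.5 | 99.5 | 50 |
| 0.8 | 99.2 | 20 |
| 1.0 | 99.0 | 0 |
| 1.2 | 98.8 | −20 |
| 2.0 | 98.0 | −100 |

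From r = 0 to r = 2 the printed result moves 100 − 98 = 2 points. The percentage moves 100 − (−100) = 200 points.

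**Baseline-subtracted AUC.** The documents give no values, so the pairs below are assumed, in arbitrary units, only to show how the ratio behaves.

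| Antagonist | Placebo | r | Difference (antagonist − placebo) | Printed: 100 − r | Factor restored: 100 × (1 − r) |
|---|---|---|---|---|---|
| −30 | −10 | 3 | −20 | 97 | −200 |
| +10 | −10 | −1 | +20 | 101 | +200 |
| −30 | +1 | −30 | −31 | 130 | +3100 |
| −30 | −1 | 30 | −29 | 70 | −2900 |

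On the corrected scale a positive result should mean a lower value under the antagonist. In the first two rows the negative placebo value reverses this: a fall of 20 reads as −200, and a rise of 20 reads as +200. The last two rows have nearly the same difference, −31 and −29, but percentages of opposite sign and very large size. Restoring the factor of 100 is therefore not enough for these endpoints.

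**The case against.** The strongest reply is that nobody would compute 99. The words before the formula say the effect is a percentage, so a reader would express the ratio in percent and get 0 for no effect; a null result of 99% would be noticed at once. This is fair as to intent, and a notation slip is the likeliest explanation. It does not make the printed rule correct, and the plan has no other definition to fall back on.

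The formula is also the last text in the document, so a trailing × 100 could have been lost when the PDF was read. The closed bracket does not rule this out: under ordinary precedence 100 − (antagonist / placebo) × 100 multiplies only the ratio and is correct. The sponsor can settle this by checking the source file. No such factor is in the available text, and the point about baseline-subtracted AUC would stand either way.

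On that second point, the plan does not expressly say the ratio will be applied to baseline-subtracted AUC, and the pairs used here are assumed, two of them with placebo values of ±1 that force extreme results. Nor does it say whether the ratio is formed per participant or from group means, which affects how often a near-zero denominator would arise. These limits mean that the frequency of the problem cannot be stated. But the formula's scope is any endpoint, and no exclusion is given.

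Finally, no test, sample size or decision in the documents depends on the formula. That stands, and it limits the consequence to reporting.

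**Conclusion.** The concern holds. As printed, the only effect formula in the plan gives 99 for no effect and compresses a 200-point range to 2 points over ratios from 0 to 2. This part is exact arithmetic and needs no assumption beyond reading the formula as it stands in the available text.

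The instability for baseline-subtracted AUC rests on two assumptions: that the formula's stated scope includes those AUCs, and that their placebo values may be near zero or negative during fasting. The plan allows the first, and the fasting design makes the second plausible.

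The formula should be corrected before results are summarised, but the error does not threaten the data or the comparison itself.

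**What to change.** Replace the formula with:

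Effect (%) = 100 × (1 − GIP(3-30)NH₂ / placebo)

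Describe it as the percentage reduction relative to placebo, since a percentage of placebo in the literal sense would be 100r. Restrict it to quantities with a positive placebo value, such as absolute AUC, and state that for these a positive result means the endpoint is lower under the antagonist. For baseline-subtracted AUC, report the within-participant difference, antagonist minus placebo; the crossover design supplies it directly.

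The cost is two lines of protocol wording, with no change to conduct, data collection or sample size.
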